After two weeks of using the first study prosthesis, participants will return to the VA for a data collection visit. Participants will be instructed to drink approximately 8 to 15 ounces of water two

hours before their study visit and to bring a pair of shorts and a t-shirt to wear, but we will provide this clothing if they prefer. We will repeat the procedures described above in the Baseline Visit to measure skin health and Socket Comfort Score.

While the prosthesis is off, we will make sure the socket and other key components are dry and we will weigh them. Participants will be provided with fresh/dry socks to wear during the procedures. Participants will be asked to change into the shirt and shorts and put the prosthesis back on. A private area to change will be provided. Participants will be asked to wear a wristwatch-style heart rate monitor during the study visit. We will also place a small absorbent pad on the calf of the intact leg to collect sweat. The pad will be attached to the skin using a sticky waterproof covering to prevent evaporation. We will also draw a mark on the skin of the residual limb at the top edge of the socket liner so we can measure how much the liner slips.

When ready, participants will enter the climate-controlled space set at 35° C (95 °F) and 50% relative humidity. Participants will sit for a 30-minute acclimation period and will then be asked to walk on a treadmill at their pre-determined self-selected walking speed for up to 30 minutes or until they feel like the prosthesis may slip off. The duration of activity will be timed, but we anticipate all participants will be able to walk for 30 minutes. Participants will be allowed to drink water as desired during the trial, and we will record the amount of fluid they drink. Handrails and a chair will be present in case participants feel unsteady or wish to take a break.

For safety purposes, we will track participants' heart rate (via the wristwatch monitor) throughout the test. For participants who do not take a beta-blocker medication (self-report), we will stop the test if their heart rate exceeds 75% of their age-adjusted maximum heart rate (220 minus age in years) for 3 consecutive minutes. For participants who do take a beta-blocker medication, we will stop the test if their heart rate exceeds 110 beats per minute for 3 consecutive minutes.

[figure not shown]

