When the treadmill walk is done, we will have participants sit and rest in a space with a comfortable climate (68 °F/20 °C, 50% relative humidity) for up to 30 minutes, and we will measure the prosthetic liner slippage. Participants will be asked to take off the prosthesis and then we will re-weigh the key components. We will also dry off participants' residual limb with an absorbent towel to collect the sweat remaining on the skin and remove the absorbent pad from the other leg. We will weigh the towels, prosthetic components, socks, and absorbent pad to see how much moisture the participants lost on their lower limbs by sweating.

We will put the step counter on participants' as-prescribed prosthesis. Participants will then be fit with their As-Prescribed prosthesis and asked to use it during their usual daily activities for the next two weeks.

Visits: As-Prescribed Prosthesis & Study Prosthesis 2

After the 2-week use period, participants will come back to the VA and, using their As-Prescribed prosthesis, they will do the same procedures they did with Study Prosthesis 1. At the end of the

visit, participants will be fit with the other study prosthesis then repeat the 2-week use period and the data collection visit.

During study sessions, visitors and observers will not be allowed in the lab unless the participant agrees to their presence; the participant can change her/his mind at any time.

Photos and Video

We may take video and photos of participants during portions of this study for documentation and use in research publications. To protect the identity and privacy of our participants, all videos and photos will be edited later to de-identify the images (e.g., blurring of faces, tattoos, and other distinguishing marks). No sound will be recorded to prevent voice identification.

Repository

Participants will be asked if they are interested in allowing their study data to be added to our de-identified data repository so that it may be used for additional research in the future. Participants who are interested will be asked to sign a separate consent form for the repository (MIRB# 00493). Once the consent form is signed, and after a PRAF to MIRB# 00493 to accept the data has been approved, a copy of the data will be added to the repository on an ongoing basis throughout the course of the study.

Payment to Participants

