A third exploratory power analysis for the transepidermal water loss ($H_{2.2}$) metric was performed, also using results reported by Choi [37]. Using the same instrument (Tewameter TM300; Courage & Khazaka, Köln, GER) proposed in our study, Choi measured transepidermal water loss as described above and found the transepidermal water loss of 16.5 ± 8.17 and 28.8 ± 18.8 g/m²/h for the controls and extrinsic atopic dermatitis children, respectively. If we assume a standard deviation of 13.0 for the difference between study prosthetic systems and a difference between means of 12.3, there is an 97% probability to find a significance difference between prosthetic systems with *20 subjects*. We note Choi reported a large difference in variances between groups (8.17 and 18.8 g/m²/h), and the power analysis is particularly sensitive to different variances. We used a value mid-way between the two groups; using a greater variance of 18.8 results in a 79% probability to find a difference with *20 subjects* while using a smaller variance of 8.17 results in a 99% probability to find a difference with *20 subjects*.

These analyses provide confidence that our proposed within-subject experimental design will provide meaningful results with a sample population of 20 subjects.

Supplemental Measures

Absorbent pads placed on the skin of the contralateral limb during the laboratory protocol will be used as a control measure of perspiration. The tar weight of the pad will be used to calculate the perspiration rate by dividing the weight of the pad by its surface area and the donned duration, expressed in grams per meter square of body surface area per hour (g m⁻² h⁻¹). We will perform a linear mixed effects regression analysis on these samples to determine if there were differences in perspiration rate across study prosthetic systems (independent variable). If a significant difference is found, we will perform an analysis of co-variance in consultation with our Center's biostatistician to quantify the effects on the study results.

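### The control sweat rate is divided by the pad's whole donned time, which includes a cool rest of unfixed length, so the same hot-chamber sweating can give different rates (minor)

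*Protocol*

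**What the plan says.** Protocol section 5.5 (Visit: Study Prosthesis 1) gives the sequence. Before chamber entry, "We will also place a small absorbent pad on the calf of the intact leg to collect sweat". The pad is sealed: "The pad will be attached to the skin using a sticky waterproof covering to prevent evaporation". In the chamber, at 35 °C and 50% humidity, "Participants will sit for a 30-minute acclimation period". They then walk at their self-selected "walking speed for up to 30 minutes or until they feel like the prosthesis may slip off". The protocol adds that "we anticipate all participants will be able to walk for 30 minutes".

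After the walk, participants sit in a room at 20 °C "for up to 30 minutes, and we will measure the prosthetic liner slippage". The prosthesis is then taken off, its components are re-weighed and the residual limb is dried. Only at that point do staff "remove the absorbent pad from the other leg".

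Protocol section 5.7 (Supplemental Measures) calls the pad a control measure of perspiration and computes its rate by "dividing the weight of the pad by its surface area and the donned duration". The rate is compared across systems in a mixed model. If the difference is significant, an analysis of covariance follows to quantify the effect on the study results, with no outcome named. The SAP mentions neither the pad, nor its rate, nor the covariance analysis.

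**The concern.** The pad is there to show whether a participant sweated to a similar degree at each visit. For that, the rate should depend on sweating in the heat and on little else. Here the denominator also contains time in a cool room, when sweating is likely to be lower, and handling time before and after. The rest has an upper limit but no fixed length, and nothing requires it to be equal at a participant's three visits. Two visits with identical sweating in the chamber can therefore yield different control rates.

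Two uses of the rate are affected. It is tested across systems to decide whether a covariance analysis is run, and it would presumably be the covariate in that analysis. H1.2, the outcome most naturally adjusted for sweating, is a weight that is not divided by time, so a rate per donned hour is on a different footing from it.

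**Working it through.** The plan states no figure for the pad rate, so there is none to reproduce. The check is direct arithmetic.

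**Inputs from protocol section 5.5**
- Acclimation: 30 min.
- Walk W: up to 30 min, with 30 expected.
- Cool rest R: 0 to 30 min.
- The pad is sealed, so its weight can only stay level or rise.

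**Assumption (not in the documents)**
- f = mean sweat rate during the rest as a fraction of the chamber average, shown for 0 to 1.

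**1. Full walk (W = 30), same hot-chamber sweat**

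Rate relative to a visit with no rest = (60 + f × R) / (60 + R).

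| Rest R | f = 0 | f = 0.25 | f = 0.5 | f = 1 |
|---|---|---|---|---|
| 20 min | 60/80 = 0.75 | 65/80 = 0.81 | 70/80 = 0.875 | 1.00 |
| 30 min | 60/90 = 0.667 | 67.5/90 = 0.75 | 75/90 = 0.833 | 1.00 |

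A 30-minute rest thus lowers the rate by 33%, 25% or 17% for f = 0, 0.25 or 0.5, and not at all for f = 1.

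**2. Early stop (f = 0)**

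Ratio for R = 30 against R = 0 = (30 + W) / (60 + W).
- W = 20: 50/80 = 0.625.
- W = 15: 45/75 = 0.60, a 40% gap.
- W = 10: 40/70 = 0.571.

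**3. Handling time**

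Suppose both visits carry the same extra wear time without sweating (f = 0, W = 30). An extra 5 min gives 65/95 = 0.684 and an extra 15 min gives 75/105 = 0.714. The gap narrows slightly but remains.

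**4. Noise if rest length is unrelated to system**

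Let R vary evenly over 0 to 30 min. Its SD is 30/√12 = 8.66 min, around a mean of 15. To first order, the SD of the log rate is 8.66 × |f/(60 + 15f) − 1/75|.
- f = 0: 8.66 × 0.01333 = 0.115.
- f = 0.25: 8.66 × 0.00941 = 0.081.
- f = 0.5: 8.66 × 0.00593 = 0.051.

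Exact values are 0.117, 0.083 and 0.052, so about 5 to 12%. Added to an assumed visit-to-visit log SD of 15%, f = 0 gives √(0.15² + 0.117²) = 0.19 and f = 0.5 gives √(0.15² + 0.052²) = 0.16.

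**5. If rest length did differ by system**

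This was simulated with no true difference in hot sweating. Assumptions: n = 20, two systems, paired t-test on log rates, between-person log SD 0.4, mean rest 15 min, rest SD 3 min. None of the gaps or visit-to-visit SDs below comes from the documents.

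| Assumed gap in mean rest | Visit-to-visit log SD | f = 0 | f = 0.25 | f = 0.5 |
|---|---|---|---|---|
| 0 min | 15% | about 5% | about 5% | about 5% |
| 2 min | 15% | 8% | 7% | 5% |
| 5 min | 15% | 26% | 15% | 9% |
| 10 min | 15% | 73% | 46% | 22% |
| 10 min | 30% | 27% | 16% | 9% |

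Entries are the share of trials with a falsely significant sweating difference, accurate to a percentage point or two. A three-system F-test with the third system mid-way gives lower figures: 65%, 39% and 17% for the 10-minute gap at 15%.

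**The case against.** The strongest reply is that no document shows rest or handling time differing by system. Section 5.5 says the later visits repeat the same procedures. Without such a difference the test across systems keeps its 5% error rate, and all that remains is noise. If actual rests are nearly constant, the noise is negligible: an SD of 3 min on about 75 min adds at most 4% (3/75), which takes 15% to √(0.15² + 0.04²) = 15.5%. The pad is also a supplemental measure, not a hypothesis endpoint. All of this stands, and it is why the point is minor.

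A second reply concerns the remedy. The prosthesis is weighed before the chamber and again after the rest, so a pad worn through the rest covers roughly the same window. Taking it off at chamber exit would break that match. This also stands and shapes the fix.

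A reader might go further and infer that the control rate moves in the opposite direction to the H1.2 grams. The documents do not support that. When only the rest lengthens from 0 to 30 min, pad grams stay level at f = 0 or rise by 12.5% (f = 0.25) to 25% (f = 0.5), while the rate falls. But these are pad grams. H1.2 concerns sweat expelled from the prosthesis, and nothing shows that rising while the participant is seated; the DAE-RED pump is activated by body weight. When the walk lengthens instead, pad grams and rate move together or the rate stays flat. Using the pad to adjust H1.2 is itself an inference, since section 5.7 names no outcome.

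**Conclusion.** The point holds as a minor one. The donned duration, as section 5.5 is ordered, contains an unstandardised cool rest plus handling time, and the SAP does not resolve this. For identical hot-chamber sweating after a full walk, rates can differ by up to 33% with no sweating in the rest. They differ by 25% or 17% with rest sweating at 25% or 50% of the chamber average, and by more after an early stop. These are extremes (0 against 30 min of rest), and the rest sweat fractions are assumed.

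The likely consequence is noise of about 5 to 12% on the log scale, if rest varies evenly over the permitted range and f lies between 0 and 0.5. A false sweating difference, and a covariance analysis triggered by it, needs rest or handling time to differ by system. The 73%, 46% and 22% figures depend on an assumed 10-minute gap and must not be read as the trial's expected error rate.

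**What to change.** - **Section 5.5:** set one rest length for all visits and remove the pad at a fixed point, such as when the prosthesis is doffed at the end of that rest. Pad and prosthesis then collect over matched windows. Record pad-on and pad-off times, and note any visit where the rest departs from the set length.
- **Section 5.7 and SAP:** state the denominator of the rate and name the outcome or outcomes to be adjusted. When the pad is a covariate for H1.2, enter total pad sweat in g per m² over the matched window, not the rate per donned hour.
- **Alternative:** remove the pad at chamber exit and divide by chamber time. The rate ratio for identical hot-chamber sweat is then 1.00. The drawback is that the control no longer covers the rest, when the prosthesis may still collect sweat. Acclimation would also need to be timed, since the protocol says only that the activity is.

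The cost is a standardised step, two recorded times and a few words in each document, with no extra visits or equipment. The SAP is written in the past tense, so visits may already be complete. In that case total g per m² can be computed from the pad weights and area already held and reported beside the rate. The limitation that rest length was not fixed should then be stated.

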5.8 Withdrawal of Subjects

This is not a treatment study; withdrawing or being terminated from this study will not have an impact on participant safety. A study clinician or the PI may withdraw a participant without their consent if he or she feels that it is not in a participant's best interest to continue in the study or the person is unable to complete the study procedures. All data previously collected from participants who withdraw or are withdrawn will be kept and may be used in the study data analysis. Participants may withdraw at any time by informing the Research Coordinator and/or the PI. If a participant wants to withdraw or we choose to withdraw a participant, while she/he are using study equipment (i.e., one of the prostheses) we will arrange for the study prosthesis to be returned/removed and the participant's as-prescribed prosthesis to be re-fit.

6. Reporting

All safety information on AEs, SAEs, unanticipated events or problems, and protocol deviations will be collected. This information will be collected at study visits and whenever subjects call to report a problem. The information will be collected on VA IRB forms (Report of a SAE and/or Problem Form, or Report of Problems (ROP) Form) and in AE log forms as needed. Safety data will be collected on an as-needed basis and will begin upon enrollment into the study. All safety reporting requirements will be followed. Any anticipated AEs will be recorded on a log sheet and reported annually with the CRQ.

If we become aware of relevant findings or information that may affect subjects' health or welfare, we will contact subjects by phone and/or a letter to notify them.

Additional Safety Monitoring

[name] (VA Puget Sound), will act as the Medical Monitor for this study. After each report of a SAE or problem, the Medical Monitor will evaluate study procedures for previously-assessed risks and will determine whether any changes must be made to minimize risks. The Medical Monitor has the authority to stop the research protocol in progress, remove individual participants from the research protocol, and take whatever steps are necessary to protect the safety and well-being of human subjects until the IRB assesses SAEs or other reports. As noted above, cumulative safety data will be reviewed yearly by the PI and the Medical Monitor and will be reported to the IRB in the Continuing Review Questionnaire (CRQ). The Medical Monitor will periodically (quarterly) have discussions with the PI about the research progress to date. The Medical Monitor will periodically (quarterly) review study enrollment, data, and procedures. The PI and the Medical Monitor will ensure security, privacy, and confidentiality by following all IRB-approved procedures. The Medical Monitor will review all unanticipated problems involving risk to subjects or others, serious adverse events and all subject deaths associated with the protocol and provide an unbiased written report of the event to the IRB. The Medical Monitor will comment on the outcomes of SAE events or problems and in the case of a serious adverse event or death, he will comment on the relationship to participation in the study. The Medical Monitor must also indicate whether he concurs with the

details of the report provided by the principal investigator. Reports for events determined by either the investigator or Medical Monitor to be possibly or definitely related to participation and reports of events resulting in death will be promptly forwarded to the CDMRP and the ORP HRPO.

7. Information Security, Privacy, and Confidentiality

As with any study, it is possible, although unlikely given the impersonal nature of the data collected, that participants may experience a loss or invasion of privacy or confidentiality because of participation in this study. The risk of harm is minimal and the protections described here will be followed.

Electronic data with PHI/sensitive information will be stored on the secure server at the VA Puget Sound. These data will only be accessed by authorized study personnel. Hardcopies of VA sensitive data and documents with PHI will be stored in a locked file cabinet in a locked office at the VA Puget Sound (Seattle). Study files/data with PHI or sensitive information will not be sent off-site. This is a locked facility to which only study investigators have access. Identifiable data will not be transmitted, transported, or stored on portable media or laptops outside of the VA, and the data will only be accessed by authorized VA study staff. We will notify the Information Security Officer of the location of the hardcopy data/files via the Data Inventory form. If study data is improperly used or disclosed we will notify the ISO and Privacy Officer within one hour of becoming aware of the issue.

Study staff will only have access to the minimum necessary identifiable information needed to perform their role. Study staff that depart the VA or are removed from the research team will be promptly removed from the research application and will no longer have access to sensitive study data.

Study data will be labeled with a study assigned code and de-identified data sets will be created/used when data is made publicly available and transmitted without restriction. A copy of de-identified data will also be made available to public search, retrieval, and analysis per the limitations the Data Management Access Plan (DMAP). The key to the code will be stored separately from the study data, and only designated VA study staff will have access to it.

The Fitbit Zip step counter and web-based app will be used to collect de-identified step count data. Researchers will set up study accounts for the application (e.g., user ID: Copatwo Studyone, [contact]), and study participants will not interact with the application. No PHI/PII will be entered when the study accounts are created. Study staff will sync the Fitbits when participants come to the VA for study visits and will pull the data from the Fitbit website. They study IDs will be securely stored in the crosswalk at the VA.

De-identified, non-sensitive electronic data labeled with the study assigned codes, and all 18 HIPAA identifiers removed or converted to de-identified format, may be stored on password-protected equipment (computers/laptops/SD cards) but will not be encrypted. De-identified data files may be

sent off-site via email, file transfer software, and/or other electronic media (CD/DVD, USB drive) to our biostatistician ([name], MS), off-site collaborator ([name], CPI), and between study investigators. Arusha Control, Inc. (off-site collaborator) will only have access to de-identified data.

Any consented photography or video will protect participants' identity (e.g., by obscuring the subject's face and any identifying marks like tattoos). The videos and photos may include the participant's entire body, but they will be anonymized during data processing; the participant's face will be blurred, any identifying marks will be covered or blurred, and then the original file will be deleted. If a participant's voice is accidentally recorded, that section of video would be altered prior to any use outside of the VA study team. The video camera and the recording media (e.g., SD cards, optical disks) will be stored in a locked office at the VA Puget Sound. Photos and videos that do not contain identifiable information may also be stored on password-protected computers for future use in scientific presentations and publications. Study records with PHI/PII will be stored until the end of the study, and for a minimum of 6 years after the study is completed (in accordance with the records retention schedule); they will be destroyed using VA approved procedures. Hard copy data with identifiable and/or sensitive information will be shredded per VA approved policies. Electronic data containing identifiable information will be wiped using VA approved software. De-identified data will be stored indefinitely.

VA medical records will be created, or updated, for each participant. The medical record will include information about enrollment in this study, cholesterol test results (if done at VA), and information about any other medical treatment received (if needed) that is related to this study. All authorized users of the national VA medical records system can have access to the medical record. This may include health insurance companies who are being billed for medical costs. This record will be kept forever.

8. Communication Plan

This is not a multi-site study. If students or staff at the University of Washington are participating as study staff at the VA, the PI will assure that the appropriate approval is obtained from the UW Human Subjects Division.

9. References

